### **Date of first administration of study drug**

The date of first administration of study drug is derived as the first date when a nonzero dose of study drug is administered. The date of first administration of study drug is also referred to as **start date of study drug**. Start date of study drug is defined for each drug which is part of study treatment, by period (induction, consolidation, maintenance, where applicable) and overall.

### **Date of last administration of study drug**

The date of last administration of study drug is defined as the last date when a nonzero dose of study drug is administered. This date is also referred to as **last date of study drug**. Last date of study drug is defined for each drug which is part of study treatment, by period (induction, consolidation, maintenance, where applicable) and overall.

### **Date of first administration of study treatment**

The date of first administration of study treatment (will be midostaurin for all patients) is derived as the first date when a nonzero dose of any component of study treatment is administered. It is derived by period (induction, consolidation, maintenance) and overall.

For example, if the 1st dose of midostaurin is taken on 08-Feb-2016, and 1st dose of a combination partner (e.g. cytarabine), is taken on 01-Feb-2016, then the date of first administration of study treatment is 01-Feb-2016. The date of first administration of study treatment is also referred to as ***start date of study treatment***.

### **Date of last administration of study treatment**

The date of last administration of study treatment is derived as the last date when a nonzero dose of any component of study treatment is administered. It is derived by period (induction, consolidation, maintenance) and overall.

For example if the last dose of midostaurin is taken on 21-Mar-2016, and the last dose of a combination partner is taken on 03-Apr-2016, then the date of last administration of study treatment is on 03-Apr-2016. This date is also referred to as ***last date of study treatment***.

### **Duration of exposure**

#### **Daunorobucin, Idarubicin and Cytarabine**

The duration of exposure for the **study drugs** will be calculated by cycle, period (induction, consolidation, maintenance, when applicable) and overall as:

- Duration of study drug exposure (days) in a **cycle** = [(date of last administration of study drug in that cycle) - (date of first administration of study drug in that cycle) + 1]
- Duration of study drug exposure (days) in a **period** = sum of durations of study drug exposure (days) in each cycle of that period
- **Overall** duration of study drug exposure (days) = sum of durations of study drug exposure (days) in each cycle

#### **Study treatment and Midostaurin**

The duration of exposure for the **study treatment and Midostaurin** will be calculated by cycle, period (induction, consolidation, maintenance) and overall as:

- Duration of study treatment/Midostaurin exposure (days) in a **cycle** = [(date of last administration of study treatment/Midostaurin in that cycle) - (date of first administration of study treatment/Midostaurin in that cycle) + 1]
- Duration of study treatment exposure (days) in a **period** = sum of durations of study trt/Mido exposure (days) in each cycle of that period.
- **Overall** duration of study treatment exposure (days) = [(date of last administration of study treatment/Midostaurin) - (date of first administration of study treatment/Midostaurin) + 1]
- If the start or end date of a study drug is missing, the duration will be missing. The durations will include periods of temporary interruption (planned or actual) for any reason.

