## 2.5.2 Study treatment and tolerability

### Study treatment

Duration of exposure (days), actual cumulative dose and actual dose intensity will be summarized by period and overall for each of the study drugs: midostaurin, daunorubicin and idarubicin for the safety set. Duration of exposure (days), actual cumulative dose and actual dose intensity will be summarized also by cycle. The number of patients with midostaurin dose changes, interruptions and permanent discontinuations will be presented by age category and overall, along with reasons for the dose change/interruption/permanent discontinuation.

Duration of midostaurin treatment exposure (days) will also be categorized and summarized by period and overall for the safety set using the following intervals:

- ≤ 20; >20; >40; >60; >120; >180; >240; >300; >360

Duration of study treatment exposure (days) will be summarized by period and overall for the safety set using the following intervals:

- ≤ 28; >28; >56; >84; >112; >196; >280; >364; >448; >532

Duration include the rest/recovery days between cycles and will be derived as the following:

Last intake of any study treatment component – first intake of any study treatment component +1

If there are more than 10 patients in each regimen exposure will be further summarized by regimen (“7+3” and “5+2”).

Data will be listed for all patients in the safety set.

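### SAP 2.1.1 and 2.5.2 give conflicting rules for study-treatment exposure by period, and the BUN and urea conversions in SAP 6.2 are not inverses

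*SAP*

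**What the plan says.** **Exposure by period.** Under Duration of exposure, SAP 2.1.1 measures each cycle from first to last administration, plus one day. Study-treatment exposure in a period is then the "sum of durations of study trt/Mido exposure (days) in each cycle of that period". Only the overall duration is a calendar span: "date of last administration of study treatment/Midostaurin) - (date of first administration of study treatment/Midostaurin) + 1".

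SAP 2.5.2 introduces the study-treatment categories with "Duration of study treatment exposure (days) will be summarized by period and overall for the safety set using the following intervals"; the cut-offs are 28, 56, 84, 112, 196, 280, 364, 448 and 532 days. It continues: "Duration include the rest/recovery days between cycles and will be derived as the following", and gives last intake of any component minus first intake plus one.

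**Start of induction exposure.** SAP 2.1.1 says "The date of first administration of study treatment (will be midostaurin for all patients) is derived as the first date when a nonzero dose", whichever drug that dose belongs to. Its example has a combination partner starting on 1 February and midostaurin on 8 February, and concludes "then the date of first administration of study treatment is 01-Feb-2016". The general definitions in 2.1.1 start the induction period at the first midostaurin dose. The study-drug definition covers only drugs used after consent, and Protocol 7.1.2 places consent after chemotherapy has begun.

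**BUN and urea.** For missing values, SAP 6.2 sets urea equal to BUN divided by 0.357, and BUN equal to urea divided by 2.1428, with every quantity in mg/dL.

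**The concern.** A sum of within-cycle spans cannot contain days that lie between cycles, whereas a first-to-last span must contain them. Both sections describe study-treatment exposure at period level, so two programmers could each follow the SAP and produce different by-period tables. The lower cut-offs are multiples of the 28-day cycle. A patient who completes n full consolidation cycles therefore sits exactly on the upper edge of a category under 2.1.1, and one recovery day moves that patient up under 2.5.2. Exposure is the context in which a safety-primary study is read, so the table should have a single definition.

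The conversion pair matters because Protocol Table 7-3 collects BUN or urea as alternatives, so one of the two may often be missing and the derivation will be used.

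**Working it through.** **Inputs.** Cycles are 28 days. A gap is counted in dose-free days, which is an assumption about how the protocol counts.
- Between induction cycles: 3 to 42 days (Protocol 7.1.4.1).
- Between consolidation cycles: at least 3 days. Protocol 7.1.4.2 implies at most 70 − 28 = 42 days after cycle 1 and 21 days after each later cycle. Protocol 7.2.1 instead asks sites to contact the sponsor beyond 56 days from the previous start, a gap of 56 − 28 = 28. The upper bounds are therefore soft.
- Maintenance cycles are contiguous (Protocol 7.1.4.3).

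The plan's own timeline confirms that recovery is not negligible. SAP 2.1.6 adds 2 + 2 + 4 + 4 + 12 + 1 = 25 months, of which 2 + 4 = 6 are recovery.

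**Full consolidation, n cycles.** Rule in 2.1.1: 28n. Rule in 2.5.2: 28n plus the gaps.

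| Cycles | 2.1.1 | 2.5.2, 3-day gaps | 2.5.2, upper (7.1.4.2) | 2.5.2, upper (7.2.1) |
|---|---|---|---|---|
| 2 | 56 | 56 + 3 = 59 | 56 + 42 = 98 | 56 + 28 = 84 |
| 3 | 84 | 84 + 6 = 90 | 84 + 63 = 147 | 84 + 56 = 140 |
| 4 | 112 | 112 + 9 = 121 | 112 + 84 = 196 | 112 + 84 = 196 |

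The 3-day gap alone carries each patient past 56, 84 or 112 days.

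**Stopping within the last consolidation cycle.** Let d be the last-dose day, g a uniform gap, and the earlier cycles be full. Rule 2.1.1 gives 28(n − 1) + d and rule 2.5.2 adds g(n − 1). The category differs when d + g(n − 1) > 28. Cytarabine is scheduled on days 1, 3 and 5 and midostaurin on days 8–28, so there are 3 + 21 = 24 possible last-dose days.

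| Gap | n = 2 | n = 3 | n = 4 |
|---|---|---|---|
| 3 days | 3 of 24 | 6 of 24 | 9 of 24 |
| 7 days | 7 of 24 | 14 of 24 | 21 of 24 |
| 14 days | 14 of 24 | 24 of 24 | 24 of 24 |

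**Two induction cycles.**
- Counted from midostaurin: 21 + 28 = 49 days under 2.1.1, against 49 + 3 = 52 to 49 + 42 = 91 under 2.5.2. The category changes only when 49 + gap > 56, that is for gaps of 8 days or more.
- Counted from chemotherapy day 1, as in the SAP example: 28 + 28 = 56, against 59 to 98. The category always changes.
- Counted from the first dose after consent, the result lies between these two.

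**Where the rules agree.** One induction cycle counted from chemotherapy day 1: 28 and 28. Twelve maintenance cycles: 336 and 336. Overall: both sections use the same span, and an unresolved start date shifts both equally.

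**BUN and urea.** Inverse formulas would need 0.357 × 2.1428 = 1; the product is 0.765. The first formula multiplies BUN by 1/0.357 = 2.801, and the second implies a factor of 2.1428. Their ratio is 2.801/2.1428 = 1.307. If the urea formula is the wrong one, derived urea is 1.307 times too large. If the BUN formula is the wrong one, derived BUN is 1.307 times too large.

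**The case against.** **Section 2.5.2 may only restate the overall rule.** Its formula carries no by-period qualifier and matches the overall formula in 2.1.1. That reading fails because the sentence introducing the categories says they apply by period as well as overall.

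**Section 2.1.1 says durations include planned or actual temporary interruptions.** That covers days inside a cycle's span. It cannot add days between cycles to a sum of cycle spans.

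**A programming specification may already settle the derivation.** The SAP introduction places variable derivations there, and that document is not available. This is possible, but the two SAP sections would still need to agree. The change log records the exposure rules as clarified on 26 June 2020 against 2.1.1 alone, and the current texts still differ.

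**The induction effect may be small.** This stands in part. The induction period is defined from the first midostaurin dose, which favours 49 against 52–91 days, where short gaps change no category.

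**A reader might infer that midostaurin dose intensity is also ill-defined**, because midostaurin duration is summed by period but is a calendar span overall. The documents do not support this. SAP 2.1.1 defines a duration at each level, and 2.5.2 reports dose intensity by period and overall and adds that "actual cumulative dose and actual dose intensity will be summarized also by cycle", so the denominator at the same level is the natural reading. Nor is comparison with chemotherapy a difficulty. Its overall "duration of study drug exposure (days) = sum of durations of study drug exposure (days) in each cycle", dose intensity is derived only for midostaurin and the anthracyclines, and anthracyclines are given only in induction, so their overall and induction figures coincide.

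**A reader might also infer that all derived BUN and urea values and their flags are wrong.** The formulas show only that at least one is. They apply only to missing values, and SAP 6.2 sets a normal range for derived calcium but none for derived BUN or urea.

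**Conclusion.** The SAP is wrong as written on two matters, and both are minor.

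First, the two by-period rules for study-treatment exposure conflict for any patient with two induction cycles or two to four consolidation cycles. Full consolidation differs by at least 3, 6 or 9 days for two, three or four cycles, and the category always changes. This rests on 28-day cycles, full adherence up to the last cycle, and gaps read as dose-free days. The upper figures of 98, 147 and 196 days use soft limits, but the conclusion needs only the 3-day minimum. Section 2.1.1 also contradicts itself on the induction start date. The number of patients affected cannot be found in the documents.

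Second, at least one BUN/urea formula is wrong. If exactly one is, values derived with it are 30.7% too high. The effect is limited to derived values in the laboratory listings and to any normal-range classification applied to them; SAP 2.9.3 plans no shift table for either analyte.

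It would go too far to infer that the main results are at risk. Primary AE proportions, CR/CRi rates and tolerability summaries do not use these derivations, and the overall exposure categories do not depend on which of the two rules is chosen. The SAP's added rest-day sentence concerns study treatment, so the separate midostaurin exposure categories are not in conflict.

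**What to change.** - State one rule for study-treatment duration by period, in the same words in SAP 2.1.1 and 2.5.2, saying explicitly whether days between cycles count.
- Reconcile the induction start date across the general definitions, the study-drug definition and the definition of first study-treatment administration in 2.1.1, and correct either the parenthesis or the example.
- Confirm one BUN/urea factor and use it in both directions in SAP 6.2.
- Re-run the by-period study-treatment exposure table and the affected laboratory listings.

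The cost is SAP wording and a limited re-run, with no new data. The latest SAP version already post-dates database lock, so the change should be dated and recorded in the CSR as made after lock.

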### **Dose interruption**

For **midostaurin**: An interruption is defined as a zero dose on one or more days between two non-zero dosing records. Any rest period as part of the regimen/schedule is not considered as an interruption e.g. Days 1 to 7 at the start of a cycle in the induction and consolidation phases is not considered as an interruption.

**For daunorubicin (or idarubicin) and cytarabine:** An interruption is defined as a zero dose administered on one or more scheduled days of administration e.g. a zero dose on Days 1, 3 or 5 for cytarabine in the consolidation phase.

Note: The last zero dose of a study drug (followed by permanent discontinuation) is not considered as a dose interruption. Additionally, two consecutive zero doses will be counted as one interruption if the reasons for these two consecutive dose interruptions are the same.

For the purpose of summarizing interruptions and reasons, in case multiple entries for interruption are entered on consecutive days with different reasons these will be counted as separate interruptions. However, if the reason is the same in these multiple entries on consecutive days, then it will be counted as one interruption.

### **Dose reduction**

A dose reduction is where the prescribed dose is lower than the previous prescribed dose or where the actual dose administered/total daily dose is lower than the prescribed dose. Any dose change to correct a dosing error will not be considered a dose reduction, e.g. if due to a dosing error, a patient receives higher than protocol planned starting dose and moves down to the planned starting dose then this is not counted as a reduction, however if they move directly from a higher than planned starting dose down to a lower than protocol planned starting dose, then this is counted as a reduction.

Note: It is assumed that if there is a dose reduction, then the 'Dose changed' box was ticked on the dose administration electronic case report form (eCRF) page.

If dose is recorded by regimen is missing or entered as 'none', it is assumed that the study drug was taken as per-protocol.

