6.1.1 Dosing regimen

Table 6-1 Dose and treatment schedule – Induction

Treatment	Dose, route and frequency (based on 28-day cycles)
Standard-dose cytarabine* with anthracycline* (idarubicin or daunorubicin) (7+3)	Ara-C:100-200 mg/m ² /day by CIVI days 1-7 (168 hours infusion) daunorubicin: 60-90 mg/m ² /day by IV push on days 1-3 Or idarubicin: 12 mg/m ² /day by IV push on days 1-3
Cytarabine* with anthracycline* (idarubicin or daunorubicin) (5+2)	Ara-C:100 mg/m ² /day by CIVI days 1-5 daunorubicin 60 mg/m ² /day by IV push on days 1-2 Or idarubicin: 12 mg/m ² /day by IV push on days 1-2
Midostaurin	50 mg (two 25 mg capsules) twice a day by mouth on days 8-28 Patients should take their doses at approximately the same time each day, and approximately 12 hours should elapse between doses. Each daily should be given with food and a glass of water (~240 mL). Patients should be instructed to swallow capsules whole and not chew capsules. If vomiting occurs, no re-dosing is allowed before the next scheduled dose.

Table 6-2 Dose and treatment schedule – Consolidation

Treatment	Dose, route and frequency (based on 28-day cycles)
Cytarabine*	1-3 g/m ² infusion over 3 hours every 12 h on days 1, 3 and 5, up to 4 cycles based on age and per investigator discretion
Midostaurin	50 mg (two 25 mg capsules) twice a day by mouth on Days 8-28. Patients should take their doses at approximately the same time each day, and approximately 12 hours should elapse between doses. Each daily should be given with food and a glass of water (~240 mL). Patients should be instructed to swallow capsules whole and not chew capsules. If vomiting occurs, no re-dosing is allowed before the next scheduled dose.

Table 6-3 Dose and treatment schedule – Maintenance

Treatment	Dose, route and frequency (based on 28-day cycles)
Midostaurin	50 mg (two 25 mg capsules) twice a day by mouth on days 1-28, for 12 cycles or until relapse, unacceptable toxicity, or death. Patients should take their doses at approximately the same time each day, and approximately 12 hours should elapse between doses. Each dose should be given with food and a glass of water (~240 mL). Patients should be instructed to swallow capsules whole and not chew capsules. If vomiting occurs, no re-dosing is allowed prior to the next scheduled dose.

*Treatment formulation availabilities depend on countries marketing authorization as a local commercial supply is used.

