6.3.2.4 Other non-hematologic toxicities

If a patient experiences other grade 3/4 non-hematologic toxicity, which is considered to be at least possibly related to midostaurin, midostaurin must be interrupted until toxicity resolves to \leq grade 1. Missed doses of midostaurin will not be made up.

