10.5.3.6 Tolerability

Tolerability will be studied in terms of dose reductions or dose interruption due to an AE. Number and percentage of patients who have a dose modification due to a treatment related adverse event will be summarized by type of dose modification (interruption, dose reduction, and permanent discontinuation).

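### The SAP's dose-reduction definition has no non-zero condition, so a held midostaurin day counts as both an interruption and a reduction

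*SAP*

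**What the plan says.** **Reduction.** SAP 2.1.1 (Dose reduction) gives two routes. One is a prescribed dose below the preceding prescribed dose; the other is "or where the actual dose administered/total daily dose is lower than the prescribed dose". The only carve-out is the correction of a dosing error. Two data notes follow. If a dose was reduced, the SAP assumes "then the 'Dose changed' box was ticked". If the dose entry is missing or recorded as none, "it is assumed that the study drug was taken as per-protocol".

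**Interruption.** For midostaurin, SAP 2.1.1 (Dose interruption) states: "An interruption is defined as a zero dose on one or more days between two non-zero dosing records". Scheduled rest days are excluded, and "The last zero dose of a study drug (followed by permanent discontinuation) is not considered as a dose interruption".

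**Outputs.** Protocol 10.5.3.6 wants modifications due to a treatment-related AE "summarized by type of dose modification (interruption, dose reduction, and permanent discontinuation"). Protocol 10.3 asks for the number of patients with dose adjustments, naming the same three types, with reasons. SAP 2.5.2 tabulates midostaurin dose changes, interruptions and permanent discontinuations, also with reasons, and limits tolerability to reductions or interruptions caused by an AE.

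**Prescribed dose.** Protocol 6.1.1 gives midostaurin in induction as "50 mg (two 25 mg capsules) twice a day by mouth on days 8-28", which is 100 mg/day.

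**The concern.** The outputs treat interruption and reduction as different things, but the definitions do not keep them apart. This matters because the protocol handles most toxicity by holding the drug. For other grade 3/4 non-hematologic toxicity in induction and consolidation, for example, "midostaurin must be interrupted until toxicity resolves to" a stated grade. Sections 6.3.2.2, 6.3.3.1, 6.3.3.2 and 6.3.3.4 also use holds. Such holds are AE-driven, so they fall inside the tolerability output. If each is also counted as a reduction, the report would present patients as dose-reduced when their drug was stopped for a time and restarted at the same dose. A reader could no longer tell from the table how often the daily dose was actually lowered.

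**Working it through.** **Inputs**
- Prescribed dose: 2 × 50 mg = 100 mg/day (protocol 6.1.1).
- Reduction, second route: actual < prescribed (SAP 2.1.1).
- Interruption: actual = 0 on a non-rest day between two non-zero records (SAP 2.1.1).
- Candidate rule: the second route becomes 0 < actual < prescribed.

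**The plan's own figure.** The only worked dose number nearby is the SAP dose-intensity example: 1300 mg / 14 days = 92.86, which rounds to the stated 92.9 mg/day. It reproduces. If 100 mg/day was prescribed in that example (an assumption), the shortfall is 14 × 100 − 1300 = 100 mg. That is either one zero day or two half-dose days.

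**Classification by day.** The dose series are illustrative, not trial data. All have 100 mg/day prescribed throughout.

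| Series | Reduction days, as written | Interruption days, as written | Reduction days, non-zero rule | Interruption days, non-zero rule |
|---|---|---|---|---|
| One zero day within 14 days (total 1300 mg) | 1 | 1 | 0 | 1 |
| Two 50 mg days within 14 days (total 1300 mg) | 2 | 0 | 2 | 0 |
| 7-day hold, then resumed at 100 mg | 7 | 7 | 0 | 7 |
| Last record zero, then discontinued | 1 | 0 | 0 | 0 |

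The non-zero rule removes the overlap and leaves the two half-dose days classified as before.

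**If the hold is recorded as a prescribed dose of zero.** The second route then fails, because 0 < 0 is false. The first route applies instead: a prescribed 0 is lower than the previous prescribed 100. The overlap remains. In addition, a later restart at a lower non-zero dose would be compared with 0 and would not register as a reduction at that point. For this reason the comparison should be with the previous non-zero prescribed dose.

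**Consequence for percentages.** On the literal rule every interruption also generates a reduction, with the same reason and the same denominator. Hence the reduction percentage ≥ the interruption percentage, whatever the true frequency of lowered doses.

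**The case against.** The best defence is that the SAP, read as a whole, intends a split. The interruption paragraph has its own counting rules for zero doses, SAP 2.5.2 lists the types separately, and reductions are linked to a Dose changed box. SAP section 1 also leaves variable derivations to a programming specification that was not available for this review. The programmed tables may therefore be right, and nobody can say from these documents that they are wrong. That part stands. It does not repair the text: the box note is an assumption about data entry, and it neither restricts reductions to ticked records nor excludes a ticked record with a zero dose.

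A reader might infer more than the documents support:
- *That every zero-dose day is affected.* Days 1-7 of induction and consolidation cycles have no prescribed midostaurin, so the actual dose cannot fall below it.
- *That vomited doses count as reductions.* Protocol 6.1.1 only bars re-dosing. Nothing says a vomited dose is treated as not administered.
- *That forgotten doses distort tolerability.* A 50 mg day does meet the reduction wording, but tolerability is limited to AE-driven modifications. Such days could reach only the general table in SAP 2.5.2, where reasons are shown.
- *That true reductions occur only under the QTc rules.* Those rules (protocol 6.3.2.3 and 6.3.3.3) contain the explicit once-daily step, but protocol 6.3.1 permits dose adjustments more generally and mentions resuming at a lower dose.

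It is also fair to say that the output is descriptive and that no hypothesis test or sample size depends on it.

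**Conclusion.** The concern holds as a defect in a definition. Two categories that the protocol requires to be reported separately overlap as written, and the final zero dose before discontinuation drops out of one category while remaining in the other. Applied literally, the error has one direction: the reduction count is too high and takes in held-and-resumed patients.

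The size cannot be stated. It depends on how many patients were interrupted and how many were truly reduced, and the documents give neither rate, so any percentage would be invented. What does follow is the bound that the reduction percentage is at least the interruption percentage. This rests on the SAP wording being programmed literally, without the Dose changed box acting as a filter.

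The reach is limited to the split by type in protocol 10.3 and 10.5.3.6 and the dose-change table in SAP 2.5.2. The SAP 2.9.1 table of AEs leading to reduction or interruption pools the two types, so the overlap cannot change it. The primary endpoint (AEs, grade 3 and 4 AEs, SAEs, AEs leading to discontinuation, deaths) does not use the reduction definition.

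**What to change.** In SAP 2.1.1 keep both routes to a reduction and add the non-zero condition to each:
- the prescribed dose is non-zero and lower than the previous non-zero prescribed dose; or
- the actual total daily dose is above zero and below the prescribed dose.

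State that zero-dose days count only as interruption or permanent discontinuation.

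The second route should not be deleted. An AE-driven lower daily dose recorded without a new prescription would then be relabelled as non-compliance, and true reductions would be under-counted. Instead, in the general table of SAP 2.5.2, show partial days not attributed to an AE or a prescriber decision, such as one forgotten dose, under their recorded reason rather than as dose reductions.

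The cost is one or two sentences and a check that the programming specification agrees. No new data are needed. If the programs already exclude zero doses, the tables do not change and only the text is corrected.
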